## **6** STUDY DESIGN

#### 6.1 Overview

This clinical trial is a phase 2b, randomized, double-blind, placebo-controlled study to evaluate the safety and efficacy of SPI-1005 in Meniere's disease. The study is planned to be conducted in adult volunteers with Meniere's Disease (probable or definitive diagnosis) with active symptoms in the months preceding study enrollment. Study participants will be randomized into three dosing arms: SPI-1005 200 mg/BID, SPI-1005 400 mg/BID, or placebo (1:1:1). This double-blind study will evaluate both safety and efficacy of the investigational treatment.

Participants aged 18-75 years, with probable or definitive Meniere's disease will undergo baseline testing to assess severity of sensorineural hearing loss, tinnitus and vertigo. This is a multicenter study that includes patients from approximately 12 US sites.

During the study, and 28 days after completion of treatment, participants will be evaluated for safety (adverse events, physical examinations, vital signs and clinical laboratory testing (CBC, serum chemistry). Trough plasma levels of ebselen and its major metabolite (2-glucuronyl selenobenzanilide) will be evaluated using liquid chromatography-mass spectrometry (LCMS) at specified visits. Additionally, plasma will be analyzed for selenium at the corresponding visits. Female participants will receive pregnancy testing at visit 1, and those found to be pregnant will be excluded from the study and monitored for adverse events.

The effect of SPI-1005 on hearing and balance will be evaluated. Hearing will be evaluated at baseline, at the end of 28 days of study treatment, and 28 days after completing study treatment. Tinnitus and vertigo will be evaluated with the Tinnitus Functional Index (TFI) and the Vertigo Symptoms Scale (VSS), respectively. These tests will be administered at baseline, on days 14 and 28

This document is confidential and proprietary to Sponsor and EA and for restricted circulation and access only. No part of it may be transmitted, reproduced, published or used by any person/s without prior written authorization.

Version No.: Final 1.0

Page 10 of 38

Sponsor Study No: SPI-1005-251

Sponsor Name: Sound Pharmaceuticals, Inc.

NLS Study Code: SPI-1005-251

Short Title of Study: SPI-1005-251 (Sound Pharmaceuticals, Inc)

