#### **Confidentiality Statement**

Statistical Analysis Plan Version No.: Final 1.0

Page 13 of 38

Sponsor Name: Sound Pharmaceuticals, Inc.

Sponsor Study No: SPI-1005-251

CRON ACUNOVA

| NLS Study Code: SPI-1005-251 | Short Title of Study: SPI-1005-251 (Sound Pharmaceuticals, Inc) |
|------------------------------|---|
|                              |   |

For categorical variables, counts and percentages will be calculated.

For continuous variables, the decimal places for n, minimum and maximum will be provided as per the reported value. Decimal places for mean, Q1, Q3 and median will be reported one decimal place more than the reported value. The decimal place for standard deviation will be reported two decimal places more than the reported value.

In all statistical tables, p-values will be reported as specified by the statistical program used, at least up to three decimal places. P-values less than 0.001 will be reported as provided by SAS®, Version 9.2 or higher (e.g. '<0.0001'). All tests will be two-sided at the  $\alpha = 0.05$  level of significance, if not stated otherwise.

In by-visit summary tables only scheduled visits will be presented. All visits (both scheduled and unscheduled) will be presented in listings.

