#### 7.2 Randomization and Blinding Process

This study is a randomized, double-blind, placebo-controlled study design. Patients will be randomized to treatment, either placebo or two different doses of SPI-1005 (1:1:1). Study center and sponsor personnel involved in the conduct and interpretation of the study will not have access to treatment codes. Laboratory personnel, and contracted designees of SPI who statistically analyze the data, will be blinded to the study treatment received by each study participant. The bioanalytical staff analyzing PK samples will be provided a copy of the random codes but will not report unblinded data until after database lock. The sponsor's medical monitor will receive each

Apart from this, the data management and biostatistics team will be blinded until the database closure. The lead statistician will receive a copy of the unblinded treatment group after the database lock upon receiving a written authorization from the head of Biometrics/Statistics Lead from Sound Pharma to unblind the study.

treatment code in individual envelopes for use in emergency unblinding.

This document is confidential and proprietary to Sponsor and EA and for restricted circulation and access only. No part of it may be transmitted, reproduced, published or used by any person/s without prior written authorization.

Version No.: Final 1.0

Page 14 of 38

Sponsor Study No: SPI-1005-251

ECRON ACUNOVA

Sponsor Name: Sound Pharmaceuticals, Inc.

NLS Study Code: SPI -1005 -251 Short Title of Stud

Short Title of Study: SPI-1005-251 (Sound Pharmaceuticals, Inc)

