#### 7.6 Sample Size Calculation

120 male and female adults with probable or definitive Meniere's disease. This Phase 2b study (SPI-1005-251), is adequately powered to demonstrate a 50% improvement in a symptom of MD using the responder analysis detailed in below with 40 study participants per treatment group.

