#### 8.3.1.1 Pure-Tone Audiometry

Pure-tone audiometry (PTA) will be measured at visit 1, visit 3 and visit 4.

Both the actual ear value and calculated change from baseline PTA data will be summarized by visits and treatment groups.

PTA data will be analyzed with a mixed-effects model for repeated measures, and a post-hoc Bonferroni correction analysis with significance set to 0.05. The calculated change of PTA data will be calculated by the difference of the actual ear value at baseline and the actual ear value at each visit post baseline. The primary assessment of PTA data will consider a  $\geq 10$  dBHL improvement from baseline as a clinically relevant response (only low frequency: 250, 500, 1000 Hz). The secondary assessments of PTA data will consider an improvement from baseline of  $\geq 10$  dBHL at two adjacent frequencies or  $\geq 20$  dBHL at one frequency as clinically relevant responses (only low frequency: 250, 500, 1000 Hz). The final processed data will be analyzed using a chi-square test or Fisher's Exact test to assess the improvement between treatment groups.

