#### 8.3.1.2 Words-in-Noise Test

The Words-in-Noise Test (WINT) will be measured at visit 1, visit 3 and visit 4.

Both the actual ear value and calculated change from baseline WINT data will be summarized by visits and treatment groups.

WINT data will be analyzed with a mixed-effects model for repeated measures, and a post-hoc Bonferroni correction analysis with significance set to 0.05. The calculated change of WINT data will be calculated by the difference of the actual ear value at baseline and the actual ear result at each visit post baseline. The primary assessment of WINT data will consider a  $\geq 10\%$  improvement from baseline as a clinically relevant response. The secondary assessments of WINT data will consider an improvement from baseline of  $\geq 20\%$  or  $\geq 4$  words as clinically relevant responses. The final processed data will be analyzed using a chi-square test or Fisher's Exact test to assess the improvement between treatment groups.

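### The five mixed models name single-step Bonferroni, although Holm on the same family keeps the same error guarantee and gains a little power

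*SAP*

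**What the plan says.** SAP Section 6.1 sets out the design: "Study participants will be randomized into three dosing arms", namely 200 mg BID, 400 mg BID and placebo, allocated 1:1:1. Section 7.6 plans 40 participants per arm. Section 7.1 makes tests two-sided at 0.05 unless stated otherwise.

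Under the heading for the primary endpoint, Section 8.3.1.1 follows the audiometry mixed model with "a post-hoc Bonferroni correction analysis with significance set to 0.05". Section 8.3.1.2 does the same: "WINT data will be analyzed with a mixed-effects model for repeated measures, and a post-hoc Bonferroni correction analysis". Sections 8.3.1.3 (TFI), 8.3.1.4 (tinnitus loudness) and 8.3.1.5 (VSS) repeat the formula. The list of tables has ITT and per-protocol post-hoc tables for each measure.

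The visible text does not say which comparisons the Bonferroni family contains. It could be two dose-v-placebo contrasts, three pairwise contrasts, or either of these multiplied by post-baseline visits (or by frequencies for audiometry). No step-down or closed procedure is mentioned.

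Each measure also has a responder comparison by chi-square or Fisher's exact test, with no stated multiplicity adjustment. The responder definitions are the primary parameters in Section 6.2.1 and the basis of the sample size in Section 7.6.

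**The concern.** Single-step Bonferroni tests every hypothesis in a family of m at 0.05/m, whatever happens to the others. Holm starts at the same level but relaxes it for the remaining hypotheses each time one is rejected. When more than one hypothesis is false, which is what a trial of two active doses hopes for, Bonferroni gives up power and buys no stronger family-wise guarantee. When two doses share one placebo arm, the two contrasts are also correlated at about 0.5, which Bonferroni ignores and step-down Dunnett uses.

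At stake is the chance of showing an effect of each dose on the continuous scale, with about 40 patients per arm.

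**Working it through.** **Inputs from the SAP.** Three arms, 1:1:1 (6.1); 40 per arm (7.6); two-sided 0.05 (7.1, 8.3.1.1 to 8.3.1.5). Degrees of freedom for a one-visit comparison: 3 × 40 − 3 = 117.

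**Assumptions, not in the documents.** True difference from placebo of d standard deviations, d from 0.3 to 1.0; equal variances; one contrast per dose at one visit; no dropout.

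**The plan's own figure.** Section 7.6 says that the study "is adequately powered to demonstrate a 50% improvement in a symptom of MD". The stated basis is the responder comparison. It gives no control rate, SD or power, and does not say whether 50% is relative or absolute. No power can be reproduced from it, and it does not concern the mixed models. Only the 40 per arm is used below.

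**Step 1: critical values (|t|, 117 df).** Unadjusted 1.980; Bonferroni for two contrasts (0.05/2 = 0.025) 2.271; Bonferroni for three (0.05/3 = 0.0167) 2.429; two-sided Dunnett for two contrasts 2.239 (simulated).

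**Step 2: dominance.** With two contrasts, Bonferroni rejects a dose if |t| > 2.271. Holm rejects it if |t| > 2.271, or if |t| > 1.980 and the other dose has |t| > 2.271. Every Bonferroni rejection is therefore a Holm rejection. Under the global null, Holm makes at least one rejection exactly when Bonferroni does. The same argument holds for any family size, including one that spans visits.

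Simulated family-wise error over the two dose-v-placebo contrasts under the global null: three-contrast Bonferroni 3.1%, two-contrast Bonferroni 4.6%, Holm on two 4.6%, step-down Dunnett 5.0%. With one dose truly active at 1.0 SD, Holm and step-down Dunnett are both at 4.9%.

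**Step 3: power per dose.** The contrast has a non-central t distribution with non-centrality d × √(40/2).

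- Bonferroni power = P(|t₁| > 2.271).
- Holm power = the same + P(1.980 < |t₁| ≤ 2.271 and |t₂| > 2.271).

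Example, d = 0.5 in both doses: non-centrality 0.5 × 4.472 = 2.236; Bonferroni power 48.8%; the second Holm term is 5.2 points; Holm power 48.8 + 5.2 = 54.0%.

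Gains in percentage points per dose, equal effects in both doses (simulation, 1,000,000 trials per scenario):

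| d | A: Holm over Bonferroni, two contrasts | B: step-down Dunnett over Bonferroni, two contrasts | C: Holm on two over Bonferroni on three | C − A: due to dropping dose v dose |
|---|---|---|---|---|
| 0.3 | 2.3 | 3.0 | 6.1 | 3.8 |
| 0.5 | 5.2 | 6.0 | 11.4 | 6.2 |
| 0.6 | 5.5 | 6.1 | 11.4 | 5.9 |
| 0.8 | 3.0 | 3.2 | 6.0 | 3.0 |
| 1.0 | 0.7 | 0.7 | 1.4 | 0.7 |

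Columns A and B isolate stepping down. Column C mixes two changes, and half or more of it comes from removing a comparison.

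**Step 4: three pairwise contrasts kept.** Holm on all three gains about 1 to 3 points per dose over three-contrast Bonferroni for d = 0.3 to 0.8 (2.3 at 0.8), and 0.7 at d = 1.0.

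**Step 5: unequal doses, against two-contrast Bonferroni.**

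- One dose active (0.4 to 0.8 SD): the active dose gains 0.1 to 0.2 points with Holm and 0.7 to 1.4 with step-down Dunnett.
- Low dose at half the high dose's effect (high dose 0.4 to 0.8 SD): with Holm, the low dose gains 3.1 to 10.3 points and the high dose 0.3 to 0.9.

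**The case against.** The strongest objections concern scope and size, and most of them stand.

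*The family is undefined.* A reader might infer that comparing three arms means dividing alpha by three, and so claim a gain of about 6 to 12 points. The SAP does not say so. That figure needs the current family to be all three pairs and also needs dose v dose to be dropped. Dropping it is a real trade-off in a two-dose Phase 2b trial, not a free gain from a better method.

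*Error control.* A reader might also infer that naming the two dose-v-placebo contrasts within each model keeps a 5% error rate. That is shown only for one measure at one visit. Audiometry and WINT have two post-baseline visits; TFI, loudness and VSS have three. If Holm were applied afresh at each visit, simulated within-model error under the global null is 8 to 9% over two visits and 11 to 13% over three (assumed between-visit correlation 0.3 to 0.7). If the present Bonferroni family already spans visits, that would loosen control. This is why the change must keep whatever family Bonferroni would cover.

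*Relevance.* The responder comparisons carry the primary parameters and the sample size, and this change does not reach them. Placement under the primary-endpoint heading does not make the continuous models the decision rule.

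*Bonferroni is valid and gives simple simultaneous intervals.* True, and this is the one real cost of leaving it.

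None of these shows a case in which Bonferroni rejects something that Holm on the same family would not.

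**Conclusion.** The point holds as a cheap improvement, not as an error in the plan. On an unchanged family, Holm is at least as powerful as the named method, with the same family-wise guarantee.

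The benefit rests on assumed effect sizes and 40 analysed patients per arm, and dropout would alter it. It is about 2 to 6 points per dose over two-contrast Bonferroni, or 1 to 3 with all three pairs in the family, when both doses have equal effects of 0.3 to 0.8 SD. It is largest for a weaker second dose, about 0 to 1 point over two-contrast Bonferroni if only one dose works, and 1 point or less with equal effects of 1.0 SD.

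It does nothing for error across the five measures, the two analysis populations or the responder tests.

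**What to change.** In SAP Sections 8.3.1.1 to 8.3.1.5, name a post-hoc Holm (step-down Bonferroni) correction in place of the Bonferroni correction, over the same contrasts and visits that Bonferroni would have covered, at two-sided family-wise 0.05. List those contrasts and visits, because either method needs them to be programmable. If the family is the two dose-v-placebo contrasts at one named visit, step-down Dunnett may be used instead. Whether 400 mg v 200 mg stays in the family is a separate, optional decision and should be stated as such.

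The cost is one sentence in each of five sections and about one line of code per model, made before unblinding. The drawback is that confidence intervals matching step-down tests are less direct. Unadjusted 95% intervals, labelled as unadjusted, can be shown, with a note that they may not agree with the adjusted tests.

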#### 8.3.1.2 Words-in-Noise Test

The Words-in-Noise Test (WINT) will be measured at visit 1, visit 3 and visit 4.

Both the actual ear value and calculated change from baseline WINT data will be summarized by visits and treatment groups.

WINT data will be analyzed with a mixed-effects model for repeated measures, and a post-hoc Bonferroni correction analysis with significance set to 0.05. The calculated change of WINT data will be calculated by the difference of the actual ear value at baseline and the actual ear result at each visit post baseline. The primary assessment of WINT data will consider a  $\geq 10\%$  improvement from baseline as a clinically relevant response. The secondary assessments of WINT data will consider an improvement from baseline of  $\geq 20\%$  or  $\geq 4$  words as clinically relevant responses. The final processed data will be analyzed using a chi-square test or Fisher's Exact test to assess the improvement between treatment groups.

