| Inclusion
Criteria                 | 
 
Adult male and female patients, 18-75 years of age at the time of enrollment.
 
Diagnosis of probable or definitive Meniere's disease by AAO-HNS 1995 criteria (Section 12.1, APPENDIX I).
 
Two of three active symptoms including vertigo or disequilibrium, fluctuating hearing loss, or tinnitus within the 3 months prior to study enrollment.
 
Hearing loss of ≥30 dBHL at either 250, 500 or 1000 Hz.
 
Voluntary consent to participate in the study.
 
Male subjects that are willing to use condoms throughout the study period and 90-days following study completion even if not fertile.
 
Females of childbearing potential should either be sexually inactive (abstinent) for 14 days prior to screening and throughout the study or be using one of the following acceptable birth control methods: 
 
IUD in place for at least 3 months prior to study; or
 
Barrier method (condom or diaphragm) with spermicide for at least 14 days prior to screening through study completion; or
 
Stable hormonal contraceptive for at least 3 months prior
 
 
 
   |  |  |  |

| SPI-1005-251: CLINICAL TRIAL SYNOPSIS |  |  |  |  |
|---------------------------------------|--|--|--|--|
|                                       | 
 
to study and through study completion; or
 
Surgical sterilization (vasectomy) of partner at least 6 months prior to study enrollment.
 
Females of non-childbearing potential should be surgically sterile (bilateral tubal ligation with surgery at least 6 months prior to study enrollment, hysterectomy, or bilateral oophorectomy at least 2 months prior to study) or be at least 1 year since last menses.
 
 |  |  |  |
| Exclusion
Criteria                 |  |  |  |  |
| Study Duration                        | Estimated duration of 12 months  |  |  |  |
| Participant
Duration               | Participation for each study participants will be approximately 8 to 12 weeks across 4 clinic visits.  |  |  |  |
| Dose &
Regimen                     | Subjects will receive either SPI-1005 or matching placebo for 28 days.
Treatment will be taken orally BID. Doses include 200 mg or 400 mg
of ebselen or matching placebo in capsule form. Two week supplies
will be provided on Clinic Visit 1 and 2.   |  |  |  |

| SPI-1005-251: CLINICAL TRIAL SYNOPSIS |   |  |  |  |
|---------------------------------------|---|--|--|--|

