## **5 STUDY OBJECTIVES**

### 5.1 Primary Objectives

- > To determine the Safety of SPI-1005 treatment in adults with Meniere's disease.
- To determine the Efficacy of SPI-1005 with the following clinically validated methods and measures (responder analysis):
  - Primary pure-tone audiometry assessment (250, 500 or 1000 Hz): Improvements from baseline of ≥10 dB at 1 frequency
  - Secondary pure-tone audiometry assessments (250, 500 or 1000 Hz): Improvements from baseline of ≥10 dB at 2 adjacent frequencies or ≥20 dB at 1 frequency
  - Primary Words-in-Noise Test assessment (0-35): Improvements from baseline of ≥10%
  - Secondary Words-in-Noise Test assessments (0-35): Improvements from baseline of ≥20% or ≥4 words
  - Tinnitus Functional Index (TFI):  $(0-100) \ge 10$  pt. reduction from baseline
  - Tinnitus Loudness: Q#2 of TFI:  $(0-10) \ge 2$  pt. reduction from baseline
  - Vertigo Symptom Scale (0-60):  $\geq 6$  pt. reduction from baseline

The responder analysis from each method and measure will be compared between treatment groups for significance.

- The efficacy of SPI-1005 treatment in adults with Meniere's disease will be based on:
  - Improvement in sensorineural hearing loss using pure-tone audiometry at 250, 500, or 1000 Hz; or

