#### 6.2.4 Exploratory Parameters

- Secondary pure-tone audiometry assessments (250, 500 or 1000 Hz): Improvements from baseline of ≥10 dB at 2 adjacent frequencies or ≥20 dB at 1 frequency
- Secondary Words-in-Noise Test assessments (0-35): Improvements from baseline of ≥20% or ≥4 words

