#### 8.1.3 Demographic Data and Baseline Characteristics

Demographic characteristics include age, gender, ethnicity. Baseline characteristics include height, weight, BMI, TFI, VSS, PTA and WINT.

Frequency and percentage will be presented for gender, ethnicity. Descriptive statistics will be presented for age (years), height (cm), weight (Kg), BMI (kg/m^2). These analyses will be performed for the Randomized, Safety, ITT and Per-Protocol populations.

Demographic and baseline characteristics will be presented in the by-patient listings. A data listing will be produced for the randomization details.

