The TFI data will be analyzed with a mixed-effects model for repeated measures, and a post-hoc Bonferroni correction analysis with significance set to 0.05. The calculated change of TFI data will be calculated as the difference of the PRO value at baseline and the PRO value at each post baseline timepoint. The improvement will be considered only if the difference between post baseline and baseline value is  $\geq 10$  pts. The final processed data will be analyzed using a chi-square test or Fisher's Exact test to assess the improvement between treatment groups.

This document is confidential and proprietary to Sponsor and EA and for restricted circulation and access only. No part of it may be transmitted, reproduced, published or used by any person/s without prior written authorization.

Statistical Analysis Plan Version No.: Final 1.0

Page 22 of 38

Sponsor Study No: SPI-1005-251 Sponsor Name: Sound Pharmaceuticals, Inc.

CRON ACUNOVA

NLS Study Code: SPI -1005 -251

Short Title of Study: SPI-1005-251 (Sound Pharmaceuticals, Inc)

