#### 8.3.1.5 Vertigo Symptom Scale

Vertigo Symptom Scale (VSS) will be measured at visit 1, visit 2, visit 3 and visit 4.

The actual patient reported outcome (PRO) value and change from baseline for VSS will be summarized by visits and treatment groups.

VSS will be analyzed for Total Scale, Vertigo/balance sub-scale and Autonomic/anxiety sub-scale. The Vertigo/balance sub-scale will be calculated as the sum of questions 1, 3, 4, 6, 8, 10, 13 and 15. The Autonomic/anxiety sub-scale will be calculated as the sum of questions 2, 5, 7, 9, 11, 12 and 14. The range for the Vertigo/balance sub-scale will be 0 - 32 and the range for Autonomic/anxiety sub-scale will be 0 - 32.

VSS data will be analyzed with a mixed-effects model for repeated measures, and a post-hoc Bonferroni correction analysis with significance set to 0.05.

The calculated change of VSS data will be calculated as the difference of the PRO value at baseline and the PRO value at each post baseline timepoint. The improvement will be considered only if the difference between post baseline and baseline value is  $\geq 6$  pts. The final processed data will be analyzed using a chi-square test or Fisher's Exact test to assess the improvement between treatment groups.

This document is confidential and proprietary to Sponsor and EA and for restricted circulation and access only. No part of it may be transmitted, reproduced, published or used by any person/s without prior written authorization.

Version No.: Final 1.0

ECRON ACUNOVA Sponsor Study No: SPI-1005-251 Sponsor Name: Sound Pharmaceuticals, Inc.

NLS Study Code: SPI-1005-251

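### The five primary responder comparisons (SAP 8.3.1.1–8.3.1.5) leave out a baseline that is already recorded and partly decides who can respond; adding it is a cheap improvement, worth about −1 to +11 power points against chi-square under assumed inputs

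*SAP*

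**What the plan says.** SAP 6.2.1 lists five responder definitions as the primary efficacy parameters, and SAP 5.1 says of them: "The responder analysis from each method and measure will be compared between treatment groups for significance". The test is the same sentence in each of 8.3.1.1 to 8.3.1.5: "The final processed data will be analyzed using a chi-square test or Fisher's Exact test to assess the improvement between treatment groups". It names no covariate or stratification factor.

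Response is always judged against the patient's own baseline. For audiometry, "The calculated change of PTA data will be calculated by the difference of the actual ear value at baseline" and the value at each later visit. For TFI, "The improvement will be considered only if the difference between post baseline and baseline value is" at least 10 points; 8.3.1.4 and 8.3.1.5 use the same form with 2 points (TL) and 6 points (VSS). WINT needs at least a 10% improvement.

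The baselines are on file: "Baseline characteristics include height, weight, BMI, TFI, VSS, PTA and WINT" (SAP 8.1.3), and TL is item 2 of the TFI. SAP 7.8 defines baseline.

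Each measure also has a second analysis of the continuous score, for example "VSS data will be analyzed with a mixed-effects model for repeated measures, and a post-hoc Bonferroni correction analysis with significance set to 0.05". No covariates are listed for it, and the SAP does not rank it against the responder test.

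**The concern.** A binary response built from a change score usually depends on where the patient started. Here part of that dependence is built into the rules, because some patients cannot respond whichever treatment they receive. The inclusion criteria do not remove them. The protocol synopsis asks for "Two of three active symptoms including vertigo or disequilibrium, fluctuating hearing loss, or tinnitus within the 3 months prior to study enrollment", so a patient may enter without tinnitus or without vertigo, and the criteria shown set a minimum score only for hearing. The Per-Protocol set drops the highest WINT baselines (SAP 7.3.4), but the ITT set, which is also used for the primary analyses, does not.

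An unadjusted test treats this predictable variation as noise. With the sample size fixed at 40 per arm, the stake is power that could be recovered without another patient, visit or measurement.

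**Working it through.** **Inputs from the documents.** 40 per group (SAP 7.6); 1:1:1 allocation (7.2); two-sided 0.05 (7.1); response thresholds (6.2.1); scale ranges WINT 0–35, TFI 0–100, TL 0–10, VSS 0–60 (5.1). Responder rates, baseline distributions and baseline/follow-up correlations are not given. Every power figure below assumes them and compares one dose with placebo, 40 v 40.

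**Step 1: who cannot respond, from the rules alone.**
- WINT, read as 10% of baseline: words needed = 0.1 × baseline, rounded up. That is 1 word at baseline 1–10, 2 at 11–20, 3 at 21–30 and 4 at 31. From 32 it is impossible, since 32 × 1.1 = 35.2 > 35.
- WINT, read as 10% of the 35 words: 0.1 × 35 = 3.5, so 4 words. This is also impossible from 32 (32 + 4 = 36), and it would duplicate part of the exploratory rule, "Improvements from baseline of ≥20% or ≥4 words".
- TFI below 10, TL below 2 and VSS below 6 cannot fall by 10, 2 and 6 points.
- PTA has no comparable floor. Only regression to the mean can link response to baseline.

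**Step 2: what such patients cost (exact enumeration of the two-arm tables).** Suppose a fraction q of each arm cannot respond and the rest respond at 30% v 60%. The observed rates are 30(1−q)% v 60(1−q)%.

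| q | Observed rates | Chi-square, everyone | Chi-square, only those able to respond |
|---|---|---|---|
| 0 | 30 v 60% | 80% | 80% |
| 10% | 27 v 54% | 71% | 74% |
| 20% | 24 v 48% | 62% | 69% |
| 30% | 21 v 42% | 52% | 63% |

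Baseline information recovers part of the loss. The true q is unknown.

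**Step 3: simulated change in power from adding baseline.** There were 90 scenarios: 5 measures × 3 baseline distributions × 3 correlations (0.9, 0.8, 0.7) × 2 models, with 3,000 null and 3,000 effect trials each and effects tuned to about 70% chi-square power. The figure is the score test from logistic regression on treatment and baseline, minus chi-square, in points.

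| Measure | With regression to the mean | Without |
|---|---|---|
| TFI | +1 to +11 | 0 to +4 |
| TL | 0 to +9 | −1 to +3 |
| VSS | +2 to +11 | +0.5 to +5 |
| WINT | +3 to +8 | −1 to +3 |
| PTA | 0 to +4 | −1 to +0.5 |

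Mean type I error was 5.2% for chi-square, 5.4% for the score test and 2.6% for Fisher. The likelihood-ratio test reached 8.8% and the Wald test fell to 0.3% when responders were few, which is why the score test is preferred. A further simulation for TFI, VSS and TL gave about 0 to +8 points for the score test, with null rejection of 4.6–5.8%.

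**Step 4: a differently built check.** Normal baseline, correlation r between baseline and improvement, 40% v 60% responders, Wald test. The power change against chi-square is −1.9 points at r = 0, −1.8 at 0.2, −1.3 at 0.3, +3.0 at 0.5 and +11.5 at 0.7. Over other assumed rates with r from 0.22 to 0.71 it runs from −1.4 to +14.3.

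**Step 5: Fisher separately.** Exact power at 40 v 60% is 45.8% for chi-square and 36.9% for Fisher, a gap of 8.9 points. At 20 v 50% it is 81.7% and 74.9%, a gap of about 7. Baseline plays no part in either gap.

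**The case against.** The strongest reply is that both planned tests are valid and that the gain depends entirely on assumed inputs. That stands. Without regression to the mean the gain is small, in the check at 40 v 60% it appears only at r of about 0.5 or more, and slight losses are possible.

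Three stronger readings are tempting, and the documents do not support them.
- *Adjustment gains 7 to 20 points against Fisher.* The simulations do show that range, but +6.7 appears at r = 0, where baseline carries no information. That part is Fisher's conservatism. By the usual convention, Fisher applies when an expected count is below 5, which at 40 v 40 means fewer than 10 or more than 70 responders in total. The chance of that is about 0.0000004 at 20 v 50% and 0.15% at 15 v 35%. The SAP states no rule for choosing, but on that convention chi-square is the comparator.
- *Adjustment is worth 50 patients per arm instead of 40.* That is the best of the 90 scenarios (SD ratio 0.893; 40/0.893² = 50). The worst gives 40/1.009² = 39.
- *The SAP ignores baseline throughout.* Baseline may enter the mixed models, whose covariates are simply not listed. These models do not replace the responder comparison, which SAP 5.1 puts to a significance test.

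Two technical objections also stand, as costs. The floor is a step while the model is linear on the logit scale. And a score test on the conditional log-odds can disagree with a marginal risk-difference interval close to 0.05.

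**Conclusion.** The point holds as a cheap improvement. The responder tests are unadjusted, the relevant baseline is recorded for every measure, and the response rules exclude some baselines from responding at all; these facts come from the documents. The size does not. About −1 to +11 points against chi-square is a range over assumed distributions and correlations, with most of the benefit in TFI, TL, VSS and WINT when regression to the mean is present, and little or none for PTA. The number of patients unable to respond is unknown. Nothing here shows that the planned tests are wrong or that a gain is certain.

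**What to change.** Before unblinding, in each of SAP 8.3.1.1–8.3.1.5:
- Make the responder comparison a logistic regression on treatment and the baseline value of the same measure (for PTA, the mean baseline threshold at 250, 500 and 1000 Hz). Take the p-value from the score test, and report the standardised risk difference with its 95% confidence interval.
- Use Fisher's exact test if any expected cell count is below 5. Keep the unadjusted proportions and the chi-square test as supportive.
- Leave the treatment-group comparisons and visits as the SAP has them.
- Define the analysed ear for PTA and WINT so that each patient contributes one observation.
- Name baseline as a covariate in the mixed model of each continuous score.

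The cost is SAP wording and standard SAS procedures; patients, visits and data are unchanged. The downside is slightly more analysis work, a logit-linear assumption for baseline, and no gain or a loss of about 1–2 points if baseline is weakly related to response.
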